## Reporting of SAE to GSK

### SAE Reporting to GSK via Electronic Data Collection Tool

- The primary mechanism for reporting SAE to GSK will be the electronic data collection tool.
- If the electronic system is unavailable for more than 24 hours, then the site will use the paper SAE data collection tool (see next section).
- The site will enter the SAE data into the electronic system as soon as it becomes available.
- The investigator or medically-qualified sub-investigator must show evidence within the eCRF (e.g., check review box, signature, etc.) of review and verification of the relationship of each SAE to study treatment (causality) within 72 hours of SAE entry into the eCRF.
- After the study is completed at a given site, the electronic data collection tool will be taken off-line to prevent the entry of new data or changes to existing data.
- If a site receives a report of a new SAE from a study participant or receives updated data on a previously reported SAE after the electronic data collection tool has been taken off-line, then the site can report this information on a paper SAE form (see next section) or to the medical monitor by telephone.
- Contacts for SAE reporting can be found in the SRM.

### SAE Reporting to GSK via Paper CRF

- Facsimile transmission of the SAE paper CRF is the preferred method to transmit this information to the medical monitor.
- In rare circumstances and in the absence of facsimile equipment, notification by telephone is acceptable with a copy of the SAE data collection tool sent by overnight mail or courier service.
- Initial notification via telephone does not replace the need for the investigator to complete and sign the SAE CRF pages within the designated reporting time frames.
- Contacts for SAE reporting can be found in the SRM.

## 12.5. Appendix 5: Contraceptive Guidance and Collection of Pregnancy Information

### Definitions

#### Woman of Childbearing Potential (WOCBP)

A woman is considered fertile following menarche and until becoming post-menopausal unless permanently sterile (see below)

#### Women in the following categories are not considered WOCBP

25. Premenarchal

26. Premenopausal female with ONE of the following:

- Documented hysterectomy
- Documented bilateral salpingectomy
- Documented bilateral oophorectomy

Note: Documentation can come from the site personnel's: review of participant's medical records, medical examination, or medical history interview.

27. Postmenopausal female

- A postmenopausal state is defined as no menses for 12 months without an alternative medical cause. A high follicle stimulating hormone (FSH) level in the postmenopausal range may be used to confirm a postmenopausal state in women not using hormonal contraception or hormonal replacement therapy (HRT). However, in the absence of 12 months of amenorrhea, a single FSH measurement is insufficient.
- Females on HRT and whose menopausal status is in doubt will be required to use one of the non-hormonal highly effective contraception methods if they wish to continue their HRT during the study. Otherwise, they must discontinue HRT to allow confirmation of postmenopausal status before study enrollment.

### Contraception Guidance

#### Male participants

Male participants with female partners of child-bearing potential are eligible to participate if they agree to ONE of the following during the protocol-defined time frame in Section 6.1:

- Are abstinent from penile-vaginal intercourse as their usual and preferred lifestyle (abstinent on a long term and persistent basis) and agree to remain abstinent
- Agree to use a male condom plus an additional method of contraception with a failure rate of <1% per year as described in [Table 2](#) when having penile-vaginal intercourse with a woman of childbearing potential

Men with a pregnant or breastfeeding partner must agree to remain abstinent from penile-vaginal intercourse or use a male condom during each episode of penile penetration during the protocol-defined time frame.

Men must refrain from donating sperm for duration of study and for 90 days after study completion.

### Female participants

Female participants of childbearing potential are not eligible to participate.

**Table 2      Highly Effective Contraceptive Methods**

Highly Effective Contraceptive Methods That Are User Dependent a Failure rate of <1% per year when used consistently and correctly.	
Combined (estrogen- and progestogen-containing ) hormonal contraception associated with inhibition of ovulation 
 
• oral
 
• intravaginal
 
• transdermal
 
	
Progestogen-only hormonal contraception associated with inhibition of ovulation 
 
• injectable
 
	
Highly Effective Methods That Are User Independent	

 
• Implantable progestogen-only hormonal contraception associated with inhibition of ovulation
 
• Intrauterine device (IUD)
 
• Intrauterine hormone-releasing system (IUS)
 
• bilateral tubal occlusion
 
	
Vasectomized partner 
(A vasectomized partner is a highly effective contraception method provided that the partner is the sole male sexual partner of the WOCBP and the absence of sperm has been confirmed. If not, an additional highly effective method of contraception should be used.)
	
Sexual abstinence 
(Sexual abstinence is considered a highly effective method only if defined as refraining from heterosexual intercourse during the entire period of risk associated with the study treatment. The reliability of sexual abstinence needs to be evaluated in relation to the duration of the study and the preferred and usual lifestyle of the participant.)
	

#### NOTES:

a. Typical use failure rates may differ from those when used consistently and correctly. Use should be consistent with local regulations regarding the use of contraceptive methods for participants in clinical studies.

## Pregnancy Testing

- Women should only be included after a negative highly sensitive urine or serum pregnancy test
- Additional pregnancy testing will be performed before each PET scan, as required locally

## Collection of Pregnancy Information

### Male participants with partners who become pregnant

- Investigator will attempt to collect pregnancy information on any male participant's female partner of a male study participant who becomes pregnant while participating in this study. This applies only to participants who receive study treatment.
- After obtaining the necessary signed informed consent from the pregnant female partner directly, the investigator will record pregnancy information on the appropriate form and submit it to GSK within 24 hours of learning of the partner's pregnancy.
- Partner will also be followed to determine the outcome of the pregnancy. Information on the status of the mother and child will be forwarded to GSK
- Generally, follow-up will be no longer than 6 to 8 weeks following the estimated delivery date. Any termination of the pregnancy will be reported regardless of fetal status (presence or absence of anomalies) or indication for procedure.

### Female Participants who become pregnant

- Investigator will collect pregnancy information on any female participant, who becomes pregnant while participating in this study.
- Information will be recorded on the appropriate form and submitted to GSK within 24 hours of learning of a participant's pregnancy.
- Participant will be followed to determine the outcome of the pregnancy. The investigator will collect follow up information on participant and neonate, which will be forwarded to GSK. Generally, follow-up will not be required for longer than 6 to 8 weeks beyond the estimated delivery date.
- Any termination of pregnancy will be reported, regardless of fetal status (presence or absence of anomalies) or indication for procedure.
- While pregnancy itself is not considered to be an AE or SAE, any pregnancy complication or elective termination of a pregnancy will be reported as an AE or SAE.
- A spontaneous abortion is always considered to be an SAE and will be reported as such.
- Any SAE occurring as a result of a post-study pregnancy which is considered reasonably related to the study treatment by the investigator, will be reported to GSK as described in [Appendix 4](#). While the investigator is not obligated to actively seek

this information in former study participants, he or she may learn of an SAE through spontaneous reporting.

Any female participant who becomes pregnant while participating will be withdrawn from the study.

## 12.6. Appendix 6: Genetics

### USE/ANALYSIS OF DNA

- Genetic variation may impact a participant's response to therapy, susceptibility, severity and progression of disease. Variable response to therapy may be due to genetic determinants that impact drug absorption, distribution, metabolism, and excretion; mechanism of action of the drug; disease etiology; and/or molecular subtype of the disease being treated. Therefore, where local regulations and IRB/IEC allow, a blood sample will be collected for DNA analysis
- DNA samples will be used for research related to GSK3008348 or IPF and related diseases. They may also be used to develop tests/assays including diagnostic tests) related to GSK3008348 (or study treatments of this drug class), and IPF. Genetic research may consist of the analysis of one or more candidate genes or the analysis of genetic markers throughout the genome [or analysis of the entire genome] (as appropriate)
- DNA samples will be analyzed if it is hypothesized that this may help further understand the clinical data.
- The samples may be analyzed as part of a multi-study assessment of genetic factors involved in the response to GSK3008348 or study treatments of this class. The results of genetic analyses may be reported in the clinical study report or in a separate study summary.
- The sponsor will store the DNA samples in a secure storage space with adequate measures to protect confidentiality.
- The samples will be retained while research on GSK3008348 (or study treatments of this class) or IPF continues but no longer than 15 years after the last visit of the last subject, or other period as per local requirements.

## 12.7. Appendix 7: Liver Safety: Required Actions and Follow-up Assessments

Phase I liver chemistry stopping criteria have been designed to assure participant safety and to evaluate liver event etiology (in alignment with the FDA premarketing clinical liver safety guidance).

<http://www.fda.gov/downloads/Drugs/GuidanceComplianceRegulatoryInformation/Guidances/UCM174090.pdf>.

### Phase I liver chemistry stopping criteria and required follow up assessments

Liver Chemistry Stopping Criteria – Liver Stopping Event	
ALT-absolute ALT $\geq$ 3xULN If ALT $\geq$ 3xULN AND bilirubin  $\geq$ 2xULN (>35% direct bilirubin) or INR $>1.5$ , Report as an SAE. See additional Actions and Follow Up Assessments listed below	
Required Actions and Follow up Assessments following Liver Stopping Event	
Actions	Follow Up Assessments

 
Report the event to GSK within 24 hours
 
Complete the liver event eCRF, and complete an SAE data collection tool if the event also meets the criteria for an SAE
 
Perform liver event follow up assessments
 
Monitor the participant until liver chemistries resolve, stabilise, or return to within baseline (see MONITORING below)
 
 
MONITORING:
 
If ALT <math>\geq</math> 3xULN AND bilirubin <math>\geq</math> 2xULN or INR <math>> 1.5</math>:
 
 
Repeat liver chemistries (include ALT, AST, alkaline phosphatase, bilirubin) and perform liver event follow up assessments within 24 hrs
 
Monitor participants twice weekly until liver chemistries resolve, stabilise or return to within baseline
 
A specialist or hepatology consultation is recommended
 
	
 
Viral hepatitis serology
 
Blood sample for pharmacokinetic (PK) analysis, obtained as soon as possible after the event, and within 36 h of last dose
 
Serum creatine phosphokinase (CPK) and lactate dehydrogenase (LDH).
 
Fractionate bilirubin, if total bilirubin <math>\geq</math> 2xULN
 
Obtain complete blood count with differential to assess eosinophilia
 
Record the appearance or worsening of clinical symptoms of liver injury, or hypersensitivity, on the AE report form
 
Record use of concomitant medications on the concomitant medications report form including acetaminophen, herbal remedies, other over the counter medications.
 
Record alcohol use on the liver event
 


If <math>ALT \geq 3 \times ULN</math> AND <math>bilirubin < 2 \times ULN</math> and <math>INR \leq 1.5</math>:
 
 
• Repeat liver chemistries (include ALT, AST, alkaline phosphatase, bilirubin) and perform liver event follow up assessments within 24-72 hrs
 
• Monitor participants weekly until liver chemistries resolve, stabilize or return to within baseline
 
	
alcohol intake case report form
 
If <math>ALT \geq 3 \times ULN</math> AND <math>bilirubin \geq 2 \times ULN</math> or <math>INR > 1.5</math>:
 
 
• Anti-nuclear antibody, anti-smooth muscle antibody, Type 1 anti-liver kidney microsomal antibodies, and quantitative total immunoglobulin G (IgG or gamma globulins).
 
• Serum acetaminophen adduct HPLC assay (quantifies potential acetaminophen contribution to liver injury in participants with definite or likely acetaminophen use in the preceding week [James, 2009]).
 
• Liver imaging (ultrasound, magnetic resonance, or computerised tomography) and /or liver biopsy to evaluate liver disease: complete Liver Imaging and/or Liver Biopsy CRF forms.
 
 
NOTE: not required in China

---	---

1. Serum bilirubin fractionation should be performed if testing is available. If serum bilirubin fractionation is not immediately available, discontinue study treatment for that participant if  $ALT \geq 3 \times ULN$  and  $bilirubin \geq 2 \times ULN$ . Additionally, if serum bilirubin fractionation testing is unavailable, **record presence of detectable urinary bilirubin on dipstick**, indicating direct bilirubin elevations and suggesting liver injury.
2. All events of  $ALT \geq 3 \times ULN$  and  $bilirubin \geq 2 \times ULN$  ( $>35\%$  direct bilirubin) or  $ALT \geq 3 \times ULN$  and  $INR > 1.5$ , if  $INR$  measured, which may indicate severe liver injury (possible 'Hy's Law'), must be reported as an SAE (excluding studies of hepatic impairment or cirrhosis);  $INR$  measurement is not required and the threshold value stated will not apply to participants receiving anticoagulants
3. Includes: Hepatitis A IgM antibody; Hepatitis B surface antigen and Hepatitis B Core Antibody (IgM); Hepatitis CRNA; Cytomegalovirus IgM antibody; Epstein-Barr viral capsid antigen IgM antibody (or if unavailable, obtain heterophile antibody or monospot testing); Hepatitis E IgM antibody

## 12.8. Appendix 8: Radiation Dose Risk Assessment

Participants will be exposed to an additional dose of ionising radiation as a consequence of their participation in this study. The ionising radiation exposure from PET and CT scanning comes from three sources. A proportion of the radiation exposure comes from the administered radioligand ( $[^{18}\text{F}]\text{-FBA-A20FMDV2}$ ). The remaining radiation dose comes from an HRCT for anatomical localisation (performed once only during the study) and low dose CT scans performed in order to correct the PET data for tissue attenuation. If the participant needs to be removed from the scanner and repositioned during the PET scan than a second low dose CT scan may be performed. The doses chosen for this study aim to deliver a minimal radiation exposure, compatible with a good quality PET and CT signal.

Each participant will have up to three PET-CT scans. The effective dose for each radioligand administration will be 3.3 mSv based on a conversion factor of 21.7  $\mu\text{Sv}/\text{MBq}$  determined from study RES116235 and a maximum administered activity of 150 MBq. A low-dose attenuation CT scan of the lung results in an effective dose of 1.2 mSv. If the participant leaves the scanner during the scan and is repositioned, the CT scan will be repeated which would result in a further effective dose of 1.2 mSv. In addition, each participant will have one HRCT scan, resulting in an effective dose of 3.8 mSv. The total effective dose to each participant will therefore be up to  $3 \times (3.3 + 2.4) + 3.8 = 20.9$  mSv. All of this exposure is over and above standard practice.

The total maximum effective dose of 20.9 mSv in this study is equivalent to approximately 9 times the average yearly exposure (2.3 mSv) from natural background radiation in the United Kingdom. The additional risk of developing a fatal malignancy as a result of these exposures has been estimated as approximately 1 in 1,000 for an adult in normal health. The reduced life expectancy of IPF patients will result in a lower risk for these individuals.

Within the UK the guidance set out by ICRP 62 is generally followed in setting research study dose constraints. The level of risk may therefore be assumed to broadly fall within the ICRP 62 intermediate Category IIb, where the benefit should be more directly aimed at the cure or prevention of disease.

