PK urine collection			x						Spot urine sample to be taken from pre-dose void. Total urine collection from pre-dose to 8 h post-dose.
Biomarker blood sample		x 	x 						13. Samples at pre-dose, and at 2 and 8 h post-dose. 14. Sample at 24 h post-dose.
PET ligand administration & PET scan					x 	x 	x 		15. At least 7 days post-first dose, and no more than 14 days before next PET scan. 16. Approx. 30 min (between 20–60 min) post-dose. 17. Approx. 24 h (between 14–28 h) post-dose. Timing of post-dose PET scans may change in Cohort 2; participants will have a max of 3 PET scans in total.
HRCT					x				
Immunogenicity blood sample					x 			x	18. Pre-PET scan.
Genetic sample	x								
AE/SAE & CV event review		x	x	x	x	x	x	x	
Concomitant medication review	x	x	x	x	x	x	x	x	

ECG: Electrocardiogram, DLCO: Diffusing capacity of the lungs for carbon monoxide, FEV1: Forced expiratory volume in 1 second, FCV: Forced vital capacity, PET: Positron emission tomography, HRCT: High resolution computed tomography, AE: Adverse event, SAE : Serious adverse event, CV: Cardiovascular, PK: Pharmacokinetics

- The timing and number of planned study assessments, including safety, pharmacokinetic, imaging, immunogenicity and biomarker assessments may be altered during the course of the study based on newly available data (e.g., to obtain data closer to the time of peak plasma concentrations) to ensure appropriate monitoring.
- Any changes in the timing or addition of time points for any planned study assessments must be documented and approved by the relevant study team member and then archived in the sponsor and site study files, but will not constitute a protocol amendment. The ethics committee will be informed of any safety issues that require alteration of the safety monitoring scheme or amendment of the information and consent form (ICF).
- Acceptable time deviation windows are listed in the Study Reference Manual (SRM).

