Participants exposed to ionising radiation as a consequence of patient's participation in this study.	
The ionising radiation exposure comes from the administered radioligand, a high resolution CT (HRCT) for anatomical localization and low dose CT scans performed in order to correct the PET data for tissue attenuation. The maximum effective dose of ionising radiation that participants in this study may be exposed to is 20.9 mSv. This is equivalent to approximately 9 times the average yearly exposure (2.3 mSv) from natural background radiation in the United Kingdom.
 
The additional risk of developing a fatal malignancy as a result of these exposures has been estimated as approximately 1 in 1,000 for an adult in normal health. The reduced life expectancy of IPF patients will result in a lower risk for these individuals.
 
Within the UK the guidance set out by International Commission on Radiological Protection (ICRP) 62 is generally followed in setting research study dose constraints. The level of risk may therefore be assumed to broadly fall within the ICRP 62 intermediate Category IIb, where the benefit should be more directly aimed at the cure or prevention of disease.
	
The study has been designed to keep the radiation dose as low as reasonably practicable whilst obtaining images of sufficient quality to meet the objectives.
 
Male participants < 50 years and female participants < 55 years will not be eligible.
 
To avoid recruitment of radiation worker or serial study volunteers, participants who have been exposed to ionising radiation in excess of 10mSv above background over the previous 3 year period as a result of occupational exposure to radiation or as a result of research studies are excluded. Clinically justified (therapeutic or diagnostic) exposures are not included in the exposure calculation. Participants are asked about any occupational exposure or previous participation in research studies at screening so that dose estimates can be obtained where necessary.
 
The study will exclude women of childbearing potential.
 
The maximal dose of ionising radiation that participants

Potential Risk of Clinical Significance	Summary of Data/Rationale for Risk	Mitigation Strategy
		in this study may be exposed to is outlined in Appendix 8 .

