- Dosing period 1: participants will have pre-dose health assessments and a pharmacogenetics sample at the clinical unit on the morning of Day 1. They will remain in the clinical unit for at least 8 h after receiving their nebulised dose for safety observations, and then return to the clinical unit on Day 2. Safety assessments will be done, and PK and exploratory biomarker samples taken.
- Baseline PET scan and HRCT scan at least 7 days after the first dose, and a maximum of 14 days before the first post-dose PET scan.
- Dosing period 2: participants will attend the clinical unit for health assessments before dosing, on Day 1 or Day –1. If participants pass the health assessments, they will attend the imaging unit, have their dose administered, and have up to 2 post-dose PET scans. Alternatively, dosing may take place at the clinical unit before the patient is transferred to the imaging unit for their PET scan, depending on the PET scan timing; however, the participant must be observed for at least 4 h post-dose without changing location. The timing of the post-dose PET scans will be determined based on emerging study data. Doses will be separated by a washout of between 7 and 28 days.

### 5.1.3. Changes to Cohorts 1 or 2

Participants in Cohorts 1 and 2 will have 2 planned dosing periods. However, if a PET scan cannot be performed (e.g. because of technical issues, PET ligand synthesis radiochemistry failure, or because the participant cannot be scanned for safety reasons), participants may repeat the visit or dosing period, and repeat procedures in order to

obtain a full dataset for each endpoint. Participants may be administered an additional dose of GSK3008348 after a 7-day washout, such that they receive a maximum of 3 single doses in total during the study. Participants will not, however, be administered an additional dose of [F]-FBA-A20FMDV2; they will receive a maximum of 3 doses of the radiotracer during the study.

If a participant experiences unexpected and/or potentially serious side effects after their first or second dose, they will be referred to the clinical site investigator for assessment and ongoing care. That may include admission to a clinical bed, if deemed appropriate by the investigator, as per routine clinical practice.

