## 9.6. Positron Emission Tomography (PET)

Before each PET scan, participants will have a low dose CT scan to provide data to enable correction of the PET data for tissue attenuation. [F]-FBA-A20FMVD2 will then be injected into a cubital or forearm vein through an intravenous cannula, and emission data acquired for up to 90 minutes. One rest period will be permitted during the scan, if required.

An additional venous cannula in a cubital or forearm vein will be used to collect blood samples throughout the PET scan for quantification of the total and unmetabolised [F]-FBA-A20FMDV2-related radioactivity in whole blood and plasma. The data will be used to derive an input function for the analysis of emission PET data. The cannula may be flushed with saline to keep it patent, if required; HepSal will not be used. At the end of the scanning day, the cannula will be removed.

At the baseline visit only, an HRCT scan will also be performed for anatomical localisation.

In the event of a problem that prevents the PET scan going ahead after the study treatment has been administered, such as a quality control failure of the synthesised tracer, the scan may be rescheduled. An additional dose of study treatment may be administered to the participant if required, at the discretion of the investigator and GSK Medical Monitor, as described in Section 5.1.3.

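### The stated maximum radiation dose of 20.9 mSv leaves out a low-dose CT taken at a PET visit that is abandoned before tracer injection and then repeated

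*Protocol*

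**What the plan says.** Protocol Appendix 8 (Section 12.8) builds the dose from three sources: the tracer, low-dose attenuation CTs and a single HRCT. It allows for a second CT at each scan: "If the participant leaves the scanner during the scan and is repositioned, the CT scan will be repeated". It then concludes "The total effective dose to each participant will therefore be up to" 20.9 mSv. The risk table in Section 3.3.1 presents the same number as a ceiling: "The maximum effective dose of ionising radiation that participants in this study may be exposed to is 20.9 mSv". Both places express it as roughly nine times UK yearly background.

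Three other places bear on whether that ceiling holds:

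- Section 9.6 fixes the order of procedures: "Before each PET scan, participants will have a low dose CT scan", and the tracer is injected after that.
- Section 5.1.3 covers scans that cannot be performed for technical, radiochemistry or safety reasons. In that event "participants may repeat the visit or dosing period, and repeat procedures". It limits study drug ("such that they receive a maximum of 3 single doses in total during the study") and tracer ("they will receive a maximum of 3 doses of the radiotracer during the study").
- The Schedule of Activities limits completed imaging: "participants will have a max of 3 PET scans in total".

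The HRCT is done once only. No section sets a limit on the number of low-dose CTs.

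**The concern.** A figure offered as the maximum should cover every exposure the protocol permits. The CT comes before the injection, so a visit can fail after the participant has received CT dose but before any tracer is given. Such a visit uses none of the three tracer doses and completes none of the three PET scans, so neither limit stops it being repeated. The repeat brings another low-dose CT, and the Appendix 8 sum has no term for the first one.

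At stake is the accuracy of a safety figure on which the background comparison rests. No analysis, decision rule or eligibility criterion depends on it.

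**Working it through.** **Inputs (Protocol Appendix 8 unless stated)**

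- Tracer: 3.3 mSv per administration (21.7 µSv/MBq × 150 MBq = 3.255 mSv, rounded up); at most 3.
- Low-dose CT: 1.2 mSv each; one per scan, plus one if the participant is repositioned.
- HRCT: 3.8 mSv, once.
- UK background: 2.3 mSv per year.
- Study drug: 2 planned doses, at most 3 (Section 5.1.3).

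**The plan's own figure**

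3 × (3.3 + 2.4) + 3.8 = 17.1 + 3.8 = 20.9 mSv, and 20.9 / 2.3 = 9.1 times background. Both reproduce. Split by source, this is 9.9 (tracer) + 7.2 (six CTs) + 3.8 (HRCT).

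**General form**

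Let *r* be the number of completed scans with repositioning (0 to 3) and *a* the number of CTs at visits abandoned before injection and later repeated. With *r* = *a* = 0 the dose is 3 × (3.3 + 1.2) + 3.8 = 17.3 mSv, so

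total = 17.3 + 1.2 × (*a* + *r*).

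This exceeds 20.9 only if 1.2 × (*a* + *r*) > 3.6, that is, if *a* + *r* > 3.

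| Repositioned scans (*r*) | *a* = 0 | *a* = 1 |
|---|---|---|
| 0 | 17.3 | 18.5 |
| 1 | 18.5 | 19.7 |
| 2 | 19.7 | 20.9 |
| 3 | 20.9 | 22.1 |

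- *r* = 3, *a* = 1: 22.1 mSv; 22.1 / 20.9 = 1.057; 22.1 / 2.3 = 9.6 times background.
- *r* = 3, *a* = 2: 17.3 + 1.2 × 5 = 23.3 mSv; 23.3 / 20.9 = 1.115; 23.3 / 2.3 = 10.1 times background.

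Rounding does not explain the gap: with the unrounded tracer dose, the stated total becomes 20.77 mSv and the one-repeat case 21.97 mSv.

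**Can two abandoned visits occur within the rules?**

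The drug limit leaves 3 − 2 = 1 repeated dosing period. The baseline visit involves no study drug, so that limit does not restrict its repeats. An illustrative timetable, counting the first dose as day 0:

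- Baseline abandoned after CT on day 7 and completed on day 8.
- Second dose on day 9, with the 30-minute scan abandoned after CT.
- Third dose on day 16, with post-dose scans completed on days 16 and 17.

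Doses are 9 and 7 days apart (window 7 to 28). Baseline is 8 days after the first dose (at least 7) and 8 days before the first post-dose scan (at most 14). Tracer doses total three. Low-dose CTs total five, or eight with three repositionings: 9.9 + 8 × 1.2 + 3.8 = 23.3 mSv.

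**The case against.** The strongest reply is that 20.9 mSv is itself the limit. Appendix 8 speaks of at most three PET-CT scans, Section 3.3.1 calls the total a maximum, and a specific ceiling can be read as restricting a general permission to repeat. This does not settle the matter. The 20.9 is derived from a list of components and is not written as a rule that would stop a repeat. Nothing says that a CT without tracer uses up one of the three PET-CT scans. If it did, the repeat that Section 5.1.3 allows in order to complete the data could be blocked.

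Second, no section describes a visit that fails between CT and injection. The quality-control example in Section 9.6 is placed after study treatment, with no reference to the CT, and a tracer failure known before the CT adds nothing. That is fair: the documents do not say when the CT is done relative to tracer release, and site imaging procedures outside them may already deal with it. But the technical and safety reasons in Section 5.1.3 do not depend on tracer release.

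Third, passing 20.9 mSv takes a compound worst case. Exclusion criterion 5 removes people who cannot lie flat and still for up to 2 hours, which makes repositioning at all three scans less likely. A participant also counts as complete with only one post-dose scan, which weakens the case for repeating a failed 24-hour scan. This stands as a point about likelihood. Even so, the protocol's own sum already assumes repositioning at every scan, so the same worst-case convention should cover the other CT exposure it permits.

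**Conclusion.** The concern holds, as a minor point. The Appendix 8 arithmetic is correct, but on the protocol's wording 20.9 mSv is not a strict ceiling. The excess is 1.2 mSv with one abandoned visit and 2.4 mSv with two, and it arises only if *a* + *r* is above three. The conclusion rests on two readings: that a visit can fail after the CT and before injection, and that such a CT does not count as one of the three PET-CT scans.

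The practical effect is small. If risk scales in proportion to dose (an assumption), the quoted fatal-malignancy risk of about 1 in 1,000 becomes about 1.06 in 1,000 with one abandoned visit. No change of ICRP category can be shown from the documents.

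**What to change.** **Preferred.** In Sections 5.1.3 and 9.6 and in Appendix 8, cap low-dose CTs at six per participant, counting those from abandoned visits, and require that the CT be done only once the tracer has been released. The cap makes 20.9 mSv a true maximum (9.9 + 7.2 + 3.8), and the sequencing rule avoids needless exposure.

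**Alternative.** State how many repeat visits are permitted and add 1.2 mSv for each: 22.1 mSv for one, 23.3 mSv for two. Update the background multiple in Section 3.3.1 and Appendix 8 to match.

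**Cost.** One or two sentences in the protocol, with any matching participant information. The cap could on rare occasions prevent a repeat scan. The alternative makes the stated maximum slightly less favourable.

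The SAP (Sections 1.1 and 3.1) records that the study stopped after Cohort 1. The useful step now is to confirm from imaging records that no participant had more than six low-dose CTs, and to correct the wording if this dose assessment is reused.
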